1. RISKS TO THE SUBJECTS

a. Human Subjects Involvement and Characteristics

Admission into the study is open to men and women and to all racial and ethnic groups, age 18-65. Twenty opioid use disordered patients will be recruited from a pool of patients receiving treatment at the Substance Treatment and Recovery (STAR) program at the Ralph H. Johnson VA Medical Center, Charleston area VA clinics, and Charleston Center. Inclusion/exclusion criteria that apply to all participants are listed below:

General Inclusion / Exclusion Criteria Inclusion Criteria

Inclusion Criteria:

- 1: Participants must be able to provide informed consent and function at an intellectual level sufficient to allow accurate completion of all assessment instruments.
- 2: Participants must meet moderate to severe DSM-5 criteria for OUD. While individuals may also meet criteria for use disorders of other substances (with the exception of alcohol or benzodiazepines), they must identify opioids as their primary substance of abuse.
- 3: Participants must report chronic pain for at least the past three months and have a Brief Pain Inventory score ≥ 3 .
- 4: Participants must be receiving Medication Assisted Treatment (MAT).

Exclusion Criteria:

- 1: Participants who are pregnant.
- 2: Participants with a history of/or current psychotic disorder.
- 3: Participants with a history of dementia or other cognitive impairment.
- 4: Participants with active suicidal ideation, or a suicide attempt within the past 90 days will be excluded.
- 5: Participants with contraindications to receiving rTMS (including a history of seizures, or any implanted metal above the neck).
- 6: Those with unstable general medical conditions.
- 7: Those who are currently using tramadol.
- 8: Those with active moderate or severe alcohol or benzodiazepine use disorder due to increased risk of seizure.

b. Sources of Materials

Research material obtained from individual participants includes questionnaires and interviews with study personnel and urine samples. Data will be collected with paper and pencil and then entered into the VA REDCap database, which is a secure, password protected web-based data collection system. Coded data will be stored separately from the informed consent and HIPAA documents. Paper records will be stored in an office in the Ralph H. Johnson VAMC that is locked when not in use. Urine samples will never be marked with any identifying information. They will be discarded once read.

c. Potential Risks and Risk Mitigation Strategies:

Potential risks of rTMS: The use of high frequency rTMS has been FDA approved for the treatment of major depressive disorder since 2008. Our stimulation parameters (3000 pulses, 10Hz, 5-Seconds on 10-Seconds off) are nearly identical to the FDA approved protocol (3000 pulses, 10Hz, 4-Seconds On, 8-Seconds off), and have been used safely in many investigations including those in depression, pain, and addictions. We chose to use the slightly longer train duration of 5-seconds rather than 4-seconds due to its safety and efficacy in many trials including our preliminary single session trial with opioid users.

The common clinical dose of rTMS in depression is 36 treatments with 3000 pulses per treatment, for a total of 108,000 pulses. We will deliver a total of 18 treatments over 5 days with 3,000 pulses per treatment, for a total of 54,000 pulses. We subsequently will be giving a substantially lower total dose to each participant than is commonly given to patients being treated for depression. Accelerated treatment paradigms (including those with 6 treatments delivered daily) have been safely delivered in both depression and addictions populations without any clear adverse effect.

Risk of Seizure: The most serious risk associated with the use of rTMS is seizure. Since the adoption and widespread use of standard safety guidelines in 1997, there has only been one documented seizure. The risk of seizure has been estimated to be less than 0.1% which is lower than the risk of seizure associated with pharmacologic antidepressants. The risk of seizure is related to the various stimulation parameters (intensity,frequency, train duration), location of application, pre-existing risk of seizure, and substance/medication factors. In the very rare event a seizure is caused, removing the coil is typically sufficient to stop the seizure, and there is no increased risk of subsequent seizure. In order to mitigate the risk of seizure we will carefully individualize the intensity of stimulus (by performing a resting motor threshold determination), treat using standard treatment protocols (used safely in other studies), and exclude potential participants at higher risk of seizure (those with a past history of seizures, those in withdrawal from alcohol or benzodiazepines, etc).

Risk of Site discomfort and headache: Two relatively common risks associated with the use of rTMS include the risk of mild transient site discomfort during treatment (most patients), and the risk of headache (Approximately 5%) following treatment. Both of these potential side effects are typically mild. In terms of mitigating site discomfort, we will slowly ramp up stimulation intensity during the first three sessions. In our experience both clinically and experimentally this is a successful strategy. Additionally, due to the anti-pain effect of rTMS, participants rapidly adjust to stimulation. In the unusual circumstance that a headache is

caused by rTMS, over the counter analgesics are sufficient to alleviate the headaches, and will be available to patients on the inpatient unit.

Potential hearing loss: The discharge of the rTMS coil generates a high-energy click that may cause cochlear damage. Humans exposed to rTMS have shown temporary increases in auditory threshold (especially at high frequencies) lasting at least 5 minutes and less than 4 hours. Foam earplugs can protect against these changes and will be worn during rTMS sessions.

Safety in the case of pregnancy: This protocol will exclude pregnant women. Pregnancy status will be confirmed as part of the standard screening process.

Pain task: The pain task may cause discomfort but will not cause injury. The task will be stopped when it becomes painful to the participant.

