rTMS. Furthermore, it is well known that in order to derive a meaningful clinical effect, the application of multiple sessions of rTMS are needed. 2: This will be the first trial testing an accelerated rTMS treatment paradigm using established rTMS doses in an addictions population. This is important as there is a clear dose response effect in rTMS, where larger doses of rTMS result in a larger clinical effect ([name] et al., 2010; McDonald et al., 2011). It is additionally important as OUD and other substance use disordered populations may be difficult to treat using the standard treatment paradigm of one session per day over several weeks. 3: This trial will be the first to use rTMS as an adjunct to standard of care opioid treatment. OUD patients, including Veterans, are difficult to engage in outpatient care. Subsequently, a treatment that encourages retention and integration early in the recovery process could have a significant impact on patient outcomes.

RESEARCH DESIGN AND METHODS

Approach Overview (Figure 3): Participants will be recruited from the Ralph H. Johnson VAMC, local VA clinics, and Charleston Center. We will collect data at one week, four weeks, and three months following rTMS completion.

[figure not shown]
Acute Phase: We will screen, consent, enroll, and assess participants during an enrollment session. Following enrollment, each participant will complete baseline measurements of opioid use, opioid craving, pain, and functioning (as outlined below). Following the enrollment session, each participant will be randomized and begin the acute treatment phase of the trial. *Participants will receive a total of six sessions of rTMS on three days during the acute phase of the study over a period of up to three weeks. A period of up to one-week in between treatment days will be allowed to maximize feasibility of intervention deliverability in this population while minimizing risk of a treatment gap that is too long to allow for a summation of effect.* On the third treatment day, pain assessments will be repeated. Craving and pain will be assessed using validated questionnaires.

Continuation Phase: Participants will return at one week, four weeks, and three months for follow-up visits to preliminarily assess the intervention's impact on opioid use, pain, and functional outcomes.

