Screening and Eligibility Assessment: Individuals will be screened by the research study intake coordinator. An initial pre-screen focused on inclusion/exclusion psychiatric diagnoses, medical status, current medication regimen, and ability and willingness to commit to completion of study procedures will be used to initially determine potential study eligibility. Interested individuals will be given a full description of the study procedures and asked to read and sign an IRB-approved informed consent form before participating in a detailed, comprehensive screening and assessment phase. To ensure subjects are not experiencing any acute effects of alcohol, individuals whose breath or saliva alcohol concentration reading exceeds the instruments margin of error (0.002%) will not be allowed to participate until their BAC is not detectable.

Diagnostic/Descriptive Assessment: The *M.I.N.I. International Neuropsychiatric Interview 7.0 for DSM 5* will be used to assess psychiatric and substance use diagnoses, including assessment of opiate use. A medical history will be collected to ensure that the individual is eligible to participate, and the VA medical record may be reviewed to verify medications. In the event that an individual is found to be ineligible, he or she will be given an appropriate referral for further medical or other necessary care. If the individual is eligible, he or she will fill out questionnaires and provide a urine sample to verify self-report of substance use. If female, the urine will first be tested for pregnancy. If the pregnancy test is negative or the individual is male, the urine will be tested for drugs of abuse. A randomization/initial rTMS visit will be scheduled.

Figure 3

rTMS=Repetitive Transcranial Magnetic

Treatment Assignment: Eligible individuals will be randomized to receive active rTMS or sham treatment. Participants will be randomized using a stratified permuted random block design with block sizes of 2 and 4; *this will be utilized to maintain treatment assignment balance throughout the treatment enrollment period based on concomitant pain medication use (yes/no).*

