Community Participation Index	Assess community functioning	X		X
ShortForm36 Health Survey: SF36	Assess quality of life	X		X
Patient Health Questionnaire nine (PHQ9)	Assess depression	X		X
Trait form of the State-Trait-Anxiety Inventory	Assess anxiety symptoms	X		X
Pittsburgh Sleep Quality Index: PSQI	Assess sleep functioning	X		X
Daily Pain Diaries (Numeric Rating Scales; NRS)	Assess pain level	X	X	X
Brief Pain Inventory: BPI	Assess pain severity and functional impairment	X	X	X
McGill Pain Inventory	Assess pain severity	X	X	X
Patient Health Questionnaire: PHQ-15	Assess health status	X		X
Treatment Services Review: TSR	Monitor services utilization	X		X
Best Guess Questionnaire	Assess rTMS blind integrity			
Adverse events	Assess tolerability of rTMS		X	

Data Management: Data will be managed using REDCap as specified in the DMAP.

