Statistical Analysis: *Study feasibility will be primarily measured by a) the total number of rTMS sessions completed (out of 18 total sessions) b) the proportion of participants completing all of the rTMS session and c) the proportion of participants completing all of the rTMS sessions as well as the follow-up visits. Study tolerability will be measured as the total number of treatment emergent adverse events. Group differences (active rTMS vs. sham rTMS) in the feasibility and tolerability measures will be estimated using generalized linear models with appropriate distributions (Negative binomial for session and AE count and logit for study treatment completion). In addition to study feasibility, efficacy measures (opioid use amounts, pain, and sleep quality) will be estimated for the entire cohort as well as estimates of between group differences. Changes in study efficacy outcomes from baseline to follow-up visits will be estimated and analyzed using appropriate statistical approaches. When parametric modeling assumptions can be made, changes over time and associated variability will be estimated between treatment groups using general linear mixed models (GLMMs). The GLMMs will allow us to estimate group-specific changes over time and overall effect sizes, along with the variation in those measures, while controlling for relevant baseline covariates (e.g. baseline craving, morphine equivalents, withdrawal). Although we will likely not be powered to detect between-group differences in binary outcomes (i.e. any drug use), such effects will be explored using generalized mixed models, and for time-to-event data (e.g. days to first opioid use), survival analysis models will be constructed. When parametric modeling assumptions do not appear to be valid, alternative (e.g. non-parametric) approaches will be used. Efficacy outcomes will also be analyzed for evidence of differential treatment effects in subgroups determined by gender, race, and ethnicity. Post-hoc exploratory analyses using GLMMs within the active rTMS group will address whether specific characteristics (e.g. demographics, baseline craving, morphine equivalents, withdrawal, PTSD) are associated with a differential treatment effect. The subgroup-specific treatment effects and corresponding confidence intervals will be constructed and will be interpreted in terms of their clinical, rather than statistical, significance, and effect size of treatment to inform future trials will be estimated.* **Missing Data and Attrition:** *Missing data in longitudinal studies can be a problematic feature but can be mitigated through study design considerations. We will make every effort to prevent attrition, e.g., telephone/text/e-mail reminders prior to visits, and reinforcing attendance at each visit. However, these methods do not ensure that all data will be collected, and appropriate analysis methods will be employed to accommodate missing data. Maximum likelihood estimation yields valid inferences assuming ignorable attrition (i.e., attrition is accounted for by covariates or the dependent variable measured prior to dropout). In addition, in keeping with the ITT, we will make every effort to continue assessments for the entire course of randomized treatment, even among those who stop participating in the study assigned intervention or fail to complete the full rTMS time course.*

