
Sample Size Justification: A total of n=20 participants (n=10 per arm) will be enrolled. We anticipate that <20% of study participants will withdraw from the study or be lost to follow-up, meaning that $\geq n=16$ participants are expected to complete the study. This sample size should allow us to assess feasibility and tolerability of the intervention, and ensure that group-specific changes will be able to be estimated in a precise fashion, with 95% confidence intervals extending ~ 0.5 standard deviation units. Similarly, the overall effect size confidence interval

will likely extend only 0.3 standard deviation units. As an exploratory and developmental project, we recognize that our final sample size will not result in a fully powered study design. Model based means and variability estimates will be derived from unadjusted and adjusted analyses and will be vital for designing a larger, more definitive trial in the context of a subsequent MERIT submission. **Relapse, Drop-Out and Clinical Deterioration:** Every effort will be made to re-engage participants who miss appointments. Clinical deterioration, such as exacerbation of psychiatric or substance use disorders, will be assessed on a case-by-case basis and appropriate care will be arranged. In the case of suicidal ideation, standard STAR program operating procedures will be followed which entails contact of on-call STAR clinicians. Participants will be considered drop outs if they do not come back for follow-up visits after three attempts to contact. With the exception of participants who formally withdraw from the study, we will attempt to assess early terminators at the time of discontinuation and at the post-treatment time points. These participants will be considered in the intent-to-treat efficacy analyses.

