2. ADEQUACY OF PROTECTION AGAINST RISKS

a. Recruitment and Informed Consent

E-consent and the first diagnostic interview, will be an option if the participant is not able to come into the laboratory for consenting (Due to COVID-19, or any other in person limiting factor). The e-consent will be emailed through REDCap and approved research personnel will go through the e-consent with the participant over the phone or over video conferencing. The participant will receive a copy of the signed e-consent by email from the research personnel.

Participants will be recruited to the study from the STAR program. The study PI, Co-I, or other qualified, IRB-approved personnel will obtain informed consent. The informed consent form includes a detailed description of the study procedures, along with statements regarding participants' rights to withdraw from the procedure at any time without consequences. The informed consent form will be explained to participants in easy-to-understand language, and participants will be instructed to read the form carefully prior to signing it. Consent will be documented by the signature of the participant on the informed consent agreement, accompanied by the signature of the individual obtaining the consent.

b. Protections Against Risks

All study participants will be closely monitored for psychiatric and medical stability. If hospitalization is indicated during one of the follow-up visits, the patient will be hospitalized at the Ralph H. Johnson VAMC or an appropriate referral will be made. All participants will be fully informed that they may withdraw from the experiment at any time without penalty.

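### The plan implies that the BPI which decides entry is also the pain baseline; if so, cohort and within-arm BPI changes include a modest fall from regression to the mean, which a Day 1 baseline would largely remove

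*Combined protocol and SAP*

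**What the plan says.** Both lists of inclusion criteria (Research Design and Methods, and Protection of Human Subjects section 1a) require participants to "report chronic pain for at least the past three months and have a Brief Pain Inventory score ≥ 3". Neither says which BPI score is meant.

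The Acute Phase paragraph says that after enrollment "each participant will complete baseline measurements of opioid use, opioid craving, pain, and functioning", and places randomization after that session. The Diagnostic/Descriptive Assessment paragraph adds: "If the individual is eligible, he or she will fill out questionnaires and provide a urine sample to verify self-report of substance use". A combined randomization and first rTMS visit is then scheduled.

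Table 1 lists the BPI (purpose: "Assess pain severity and functional impairment") at Screening, at TMS Sessions 1-3 and at follow-up. It has no separate baseline column, so Screening is the only column before treatment.

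Statistical Analysis plans pain estimates for the whole cohort as well as between groups. It states that "Changes in study efficacy outcomes from baseline to follow-up visits will be estimated", without tying baseline to a visit. Sample Size Justification expects that "group-specific changes will be able to be estimated in a precise fashion", and intends the model-based means and variability to inform the design of a larger trial.

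**The concern.** When people are admitted because a fluctuating score is at or above a cutoff on a given day, some are admitted on a reading above their usual level. Their next reading is lower on average with no treatment at all. If change is measured from the admitting reading, that fall is counted as improvement.

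In a randomized trial this affects both arms equally, so the treatment contrast is safe. The plan also wants whole-cohort and group-specific changes as outputs, and those have no such protection. The bias has one direction, does not shrink as more participants are added, and makes both active and sham responses look larger.

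**Working it through.** **Is the screening BPI the baseline?** No sentence says so, so the passages have to be set side by side.

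- The Acute Phase paragraph puts baseline pain and functioning before randomization. Table 1 offers only the Screening column there.
- The community reintegration, community participation and SF36 scales appear in Table 1 only at Screening and follow-up. Their baseline must therefore be the screening visit, which supports reading the BPI the same way.
- The Diagnostic/Descriptive Assessment paragraph puts questionnaires after the eligibility decision, but that decision itself needs a BPI score. Either that score is the baseline, or there is a second BPI that Table 1 does not show separately.

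The inference is strong but not certain.

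**Size if it is.** The plan gives no figure for regression to the mean to reproduce. The only input from the documents is the cutoff of 3. The rest are assumptions: a normally distributed score, SD 2, mean 4 to 6 among those screened, and test-retest correlation r of 0.5 to 0.8.

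Expected fall = (1 − r) × SD × φ(a) / [1 − Φ(a)], with a = (3 − mean) / SD.

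Middle case, mean 5 and r = 0.7:

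- a = (3 − 5)/2 = −1
- φ(a)/[1 − Φ(a)] = 0.242/0.841 = 0.288
- fall = 0.3 × 2 × 0.288 = 0.17 points, or 0.17/2 = 0.09 SD

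| Mean screened | Share excluded by cutoff | Ratio φ/(1 − Φ) | r = 0.8 | r = 0.7 | r = 0.6 | r = 0.5 |
|---|---|---|---|---|---|---|
| 4 | 31% | 0.509 | 0.20 | 0.31 | 0.41 | 0.51 |
| 5 | 16% | 0.288 | 0.12 | 0.17 | 0.23 | 0.29 |
| 6 | 7% | 0.139 | 0.06 | 0.08 | 0.11 | 0.14 |

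The last four columns are the expected fall in points. The range 0.06 to 0.51 points is 0.03 to 0.25 SD. These use the SD of 2 before selection. In the middle case the SD among those admitted is about 1.59, so 0.17 points is 0.17/1.59 = 0.11 of the enrolled SD.

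The assumed SD matters too: the middle case becomes 0.08 points with SD 1.5 and 0.28 with SD 2.5.

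**Does a later baseline remove it?** A simulation of 2,000,000 screened people (mean 5, SD 2, r = 0.7, entry at 3 or more, no treatment effect, independent errors at each visit) gave:

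- screening to follow-up: −0.17 points
- Day 1 to follow-up: 0.00 points
- active minus sham, from the screening baseline: 0.00 points

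If errors at screening and Day 1 are correlated, some of the artefact remains.

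**The case against.** The strongest objection is that the premise is inferred. The documents take baseline measures after enrollment and questionnaires after eligibility, which leaves room for a qualifying BPI followed by a separate baseline BPI. This stands as a limit on certainty. A second reading in the same session would, however, share that day's pain level and keep part of the artefact, and the analysis text ties baseline to no visit on either reading.

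Second, the BPI is not named as the pain outcome. Daily numeric-rating diaries and the McGill inventory are also scheduled; they would regress only as far as they correlate with the BPI. Quantitative sensory testing starts on treatment Day 1 and is outside the problem. The calculation therefore applies to BPI-to-BPI change only.

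Third, the artefact is small next to the noise. At r = 0.7 and n = 10 per arm, the 95% half-width for a within-arm change is √(2 × 0.3) × 2.262/√10 = 0.55 SD, against an artefact of 0.09 SD. That stands and is a reason for low severity.

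A reader might infer more than the documents support:

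- **Half the claimed precision is lost.** Setting 0.25 SD against the stated half-width of about 0.5 SD needs mean 4 and r = 0.5 together. The 0.5 SD also does not follow from 10 per arm without further assumptions (1.96/√10 = 0.62).
- **The baseline is collected remotely.** Section 2a says "E-consent and the first diagnostic interview, will be an option if the participant is not able to come into the laboratory". It does not mention the BPI, and the questionnaires are paired with a urine sample, which suggests attendance in person.
- **Participants overstate pain to qualify.** Nothing indicates that they are told the cutoff.
- **The next trial will be planned on a sham response that is too large.** If that trial keeps the same entry rule and baseline, the same regression recurs and the observed sham change is the right planning value. The figure misleads only if either one changes.

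**Conclusion.** The point holds conditionally and at low severity. If the screening BPI is the pain baseline, as the Acute Phase paragraph and Table 1 imply without stating, whole-cohort and within-arm BPI changes include a fall of about 0.17 points (0.09 SD) under assumed mean 5, SD 2 and r = 0.7. The range is 0.06 to 0.51 points over the means and correlations examined. The cutoff is confirmed by the documents; the distribution and correlation are assumed.

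A reader might infer that the sham-controlled comparison is compromised. It is not: both arms pass the same entry test before randomization, so the expected effect on active minus sham is zero. The point is nevertheless more than a missing detail, because a scheduled measurement can remove most of a one-directional bias from outputs that the sponsor intends to reuse.

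**What to change.** - State that the screening BPI is used for eligibility only.
- Define the baseline for BPI change scores and mixed models as the treatment Day 1 BPI, completed before the first stimulation and before the participant could learn the allocation. Both conditions must be written down: Table 1 places a BPI in the TMS column without giving its timing, and Day 1 is also the randomization visit.
- Name the BPI score used for the entry test and the one used as outcome.
- State that within-arm and cohort changes describe course over time and are not estimates of treatment effect.

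The cost is a sentence or so in the protocol and in Statistical Analysis, with no added assessment. The small downside is that staff must fix the Day 1 order of events. Anyone without a Day 1 BPI would fall back on the screening value, which keeps the artefact for that person; the number of such participants should be reported.

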Recruitment: Participants will be recruited from the Ralph H. Johnson VA Medical Center, other local VA clinics, Charleston Center, and through community and online advertising. Co-I [name] is Medical Director of the STAR program and will assist in participant referrals. CPRS chart review will also be utilized. Approximately four Veterans per month are initiated on buprenorphine medication assisted treatment (MAT), the majority (77%) of which endorse chronic pain. As such, we do not anticipate any issue meeting recruitment goals for this pilot project; however, feasibility of recruitment will be assessed as an aim in this project.

Integration of Study Procedures into Standard Care: Outpatient care for includes a combination of pharmacotherapy, psychotherapy, and social work interventions. Pharmacotherapy consists of medication assisted therapy, typically buprenorphine/naloxone. The study procedures will not interfere with this standard MAT treatment or other interventions. Patients being treated for OUD commonly have co-morbid symptoms of depression and anxiety (Gros et al., 2013); as such, antidepressant treatment will be allowed to enhance generalizability.

Figure 2. Change in pain thresholds ± SEM

[figure not shown]
Inclusion Criteria: 1: Be able to provide informed consent and function at an intellectual level sufficient to allow accurate completion of assessments. 2: Meet moderate to severe DSM-5 criteria for OUD. Individuals may also meet criteria for other substance use disorders (with the exception of alcohol or benzodiazepines), but must identify opioids as their primary substance of abuse. 3: Report chronic pain for at least the past three months and have a Brief Pain Inventory Score ≥ 3 . 4: Participants must be receiving Medication Assisted Treatment (MAT).

Exclusion Criteria: 1: Pregnancy. 2: History of/or current psychotic disorder. 3: History of dementia or other cognitive impairment. 4: Active suicidal ideation, or a suicide attempt within the past 90 days. 5: Contraindications to receiving rTMS (including a history of seizures, or any implanted metal above the neck). 6: Unstable general medical conditions. 7: Current use of tramadol. 8: Active moderate or severe alcohol or benzodiazepine use disorder due to increased risk of seizure.

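### The seizure-risk section says people in alcohol or benzodiazepine withdrawal are excluded, but neither criteria list names withdrawal, and inclusion 2 and exclusion 8 leave the use-disorder threshold unclear

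*Combined protocol and SAP*

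**What the plan says.** Three places in the combined protocol and SAP bear on this point.

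- **Protection of Human Subjects, section 1c, Risk of Seizure.** Seizure is named as the most serious risk of rTMS. Three measures are offered against it: setting the intensity for each person by motor threshold, using established treatment protocols, and selecting participants. On selection, the study will keep out people at higher seizure risk; its open list of examples gives past seizures and "those in withdrawal from alcohol or benzodiazepines".
- **Inclusion 2.** In Research Design and Methods it reads "Individuals may also meet criteria for other substance use disorders (with the exception of alcohol or benzodiazepines". In section 1a of Protection of Human Subjects it reads "While individuals may also meet criteria for use disorders of other substances (with the exception of alcohol or benzodiazepines". Neither copy gives a severity limit.
- **Exclusion 8.** The two copies read "Active moderate or severe alcohol or benzodiazepine use disorder due to increased risk of seizure" and "Those with active moderate or severe alcohol or benzodiazepine use disorder due to increased risk of seizure". Both carry the qualifiers of activity and severity.

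Exclusion 5, the nearest listed criterion, is "Participants with contraindications to receiving rTMS (including a history of seizures, or any implanted metal above the neck". Exclusion 6 is a general exclusion for medical instability. Section 1a introduces its list as binding on every participant.

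**The concern.** A screener works from the criteria list. The risk section gives two examples of people to be kept out for seizure risk. One, past seizures, is written into both lists; the other, withdrawal, is in neither. A protection that the protocol says it applies, against the risk it ranks highest, therefore rests on individual judgement.

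The second problem lies inside the lists. Inclusion 2 and exclusion 8 address the same two substances, and exclusion 8 gives seizure risk as its reason, yet they draw the line in different places. A reader cannot tell whether any alcohol or benzodiazepine use disorder is meant to be disqualifying, or only the more severe current forms. At stake are consistent application of a safety criterion and a clear description of the enrolled population.

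**Working it through.** No arithmetic applies beyond a count, and the plan states no figure to reproduce. The check sets the texts side by side.

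**Step 1: is withdrawal named in either list?** Each list has 4 inclusion and 8 exclusion criteria, 4 + 8 = 12. Criteria naming alcohol or benzodiazepine withdrawal: 0 of 12. The second list restates the first, so it is the same gap in two copies, not two independent omissions.

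**Step 2: does anything else in the plan cover it?**

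- The breath or saliva alcohol test under Screening and Eligibility Assessment is aimed at current intoxication. A person in withdrawal can have no detectable alcohol.
- The pre-screen covers medical status and current medications. A medical history is taken, and the VA record may be reviewed to verify medications. These could bring withdrawal to light, but no decision rule is attached to them.
- Table 1 schedules the Timeline Follow-Back, urine drug screen and breathalyzer at screening and at the TMS sessions. It lists no withdrawal assessment. Treatment may extend over up to three weeks.
- Elsewhere, withdrawal as a clinical state appears only as opioid withdrawal in the Background and as a baseline covariate or characteristic in the Statistical Analysis section.

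**Step 3: how does each kind of candidate fare?**

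| Candidate | Inclusion 2 | Exclusion 8 | Exclusions 5 and 6 | Risk section |
|---|---|---|---|---|
| Past seizures | not addressed | not addressed | barred by 5, by name | excluded, by name |
| Active moderate or severe alcohol or benzodiazepine use disorder | not permitted | barred | not needed | not named |
| Mild current disorder | not permitted, read literally | not barred | not named | not named |
| Disorder in remission | not addressed (present tense) | not barred (must be active) | not named | not named |
| In withdrawal, no current use disorder | not addressed | not addressed | only by interpretation | excluded, by name |

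Only the first row is fully consistent between the lists and the risk section. The last row is the gap: the risk section is explicit and the lists leave it to interpretation.

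**Step 4: do inclusion 2 and exclusion 8 conflict?** A participant must meet every inclusion criterion and no exclusion criterion. The stricter rule therefore governs, and a person with mild disorder fails on inclusion 2. Everyone caught by exclusion 8 has already failed inclusion 2, so exclusion 8 and its severity limit remove nobody further. Either the limit is redundant, or it reflects the real intent and inclusion 2 is broader than meant. The text does not say which.

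**The case against.** The strongest reply is that the lists can already reach a person in withdrawal. Exclusion 5 covers contraindications to rTMS and introduces its examples with the word including, so they are not exhaustive. The risk section shows that the protocol regards withdrawal as raising seizure risk, so a screener could properly exclude under criterion 5, or under criterion 6. This stands, and it limits the point. A reader might infer that someone in withdrawal without a use disorder, for example when coming off a prescribed benzodiazepine, would pass both lists and be treated. The documents do not support that. They show only that no criterion names withdrawal.

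A reader might also infer that the seizure mitigation as a whole does not work. That goes too far as well. Withdrawal is one example, in a list left open, within one of three measures, and the other example is in both lists. The screening information in step 2 is also relevant, though it is not a withdrawal assessment.

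On the use-disorder threshold, it is fair to say that the two criteria do not collide when both are applied. The tempting claim that screeners would reach opposite decisions requires one of them to set inclusion 2 aside. Nor does either criterion naturally read as barring a disorder in remission; the plan simply does not say.

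Finally, the withdrawal wording may be one symptom of a risk section that was not aligned with the current design. The same section describes 3,000-pulse treatments at 10 Hz and 18 treatments over 5 days, whereas Research Design and Methods describes six sessions on three days with 600 pulses each. Those passages also need reconciling. That does not remove the present gap, because correcting the stimulation figures would leave the criteria lists unchanged.

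**Conclusion.** The point holds in a limited form. The protocol states a safety exclusion that the lists governing enrolment do not name. It also gives alcohol and benzodiazepine use disorder two different thresholds, one of which has no effect when inclusion 2 is read literally.

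The size cannot be put in numbers. The documents do not say how many candidates would be in withdrawal or have mild disorder, and with 20 participants planned, any share would rest on an invented count. No analysis or estimate is shown to change. What supports acting is the nature of the risk, which the protocol ranks as its most serious, and the low cost of correction.

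The conclusion assumes that screeners work from the numbered lists and that no separate screening document, outside the material reviewed, already spells out the withdrawal rule.

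**What to change.** Reconcile three places: the criteria in Research Design and Methods, the criteria in section 1a of Protection of Human Subjects, and the Risk of Seizure text in section 1c.

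1. State the position on alcohol and benzodiazepine withdrawal in the same words in both lists and in the risk section, so that the rule the risk section relies on in part is one a screener can apply without interpreting exclusion 5 or 6.
2. Make inclusion 2 and exclusion 8 express one threshold, explicit about severity and about current versus past disorder.

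Which clinical rule applies is for the sponsor and investigator to decide; this review proposes none. The cost is a change of protocol wording and, depending on the rule chosen, possibly slightly fewer eligible candidates.
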